# 5.4. REMOVAL, REPLACEMENT OR EARLY WITHDRAWAL OF SUBJECTS FROM ASSESSMENT NOT DUE TO INTOLERABLE SIDE EFFECTS

In the first and second cohorts, if only one subject is withdrawn or removed from the study, and no more than one subject experience intolerable side effects, then the subject will not be replaced. If more than one subject is withdrawn or removed from the study, and more than one subject experience intolerable side effects, then the subject will be replaced by new subject.

In the third and fourth cohort, any withdrawal or removal not due to intolerable side effects within the first 28 days will be replaced by a new subject.

#### 6. STUDY PROCEDURES AND ASSESSMENT

#### 6.1. DEFINITIONS OF STUDY PROCEDURES

#### 6.1.1. Informed Consent

Prior to initiation of any study procedures, each subject will undergo an Informed Consent process in which the subject voluntarily confirms their willingness to participate in the trial, after having been informed of all aspects of the trial relevant to their decision to participate. The investigator, or a person designated by the investigator, will fully inform the subject of all pertinent aspects of the trial. In addition, the investigator, or a person designated by the investigator, will inform the subject that he is free to refuse to enter the study or to withdraw from the study at any time, for any reason.

The Informed Consent Form (ICF) approved by the IRB/EC will contain a description of the study's purpose, procedures, inconveniences and potential risks, and anticipated benefits.

Prior to a subject's participation in the trial, an ICF will be signed and personally dated by the subject and initialed by the person who conducted the Informed Consent discussion.

If a subject is unable to read, an impartial witness should be present during the entire Informed Consent discussion. After the written Informed Consent form is read and explained to the subject and after the subject has orally consented to participating in the trial and, if capable of doing so, has signed and personally dated the Informed Consent form, the witness should sign and personally date the ICF. By signing the ICF, the witness attests that the information in the ICF was accurately explained to, and apparently understood by, the subject and that Informed Consent was freely given by the subject.

Prior to participation in the trial, the subject will receive a copy of the signed and dated written ICF. During participation in the trial, the subject will receive a copy of the signed and dated consent form updates and a copy of any amendments to the written information provided to subjects.

The investigator should document in the source data that the Informed Consent was signed prior to subject's participation in the study and according to the ICH guidelines, as described above.

## 6.1.2. Medical History

Subjects' medical history should be fully documented at screening Day 1 (28 through 7days prior to baseline), to ensure compliance with study inclusion criteria and the absence of circumstance mentioned in the exclusion criteria. Medical history information must include, but not be limited to past and present medical conditions, concomitant non-drug treatments and hypersensitivity to drugs.

#### 6.1.3. Concomitant Medication

All concomitant medication given 3 months prior to study entry, including blood and blood products dietary supplements, and non-prescription drugs will be listed at screening/baseline. Each entry will include the treatment's start date, treatment name (Generic), reason for use, dosing regimen (dose and frequency of use), route of administration, and stop date (if applicable). The clinical significance of the medication use will be decided by the investigator. Study subjects will be routinely questioned for changes in the administration of concomitant medication during the trial.

## 6.1.4. Physical Examination

The investigator (or medically qualified nominee) will conduct a complete physical examination at screening Day 1 (performed 28 through 7 days prior to baseline). Clinically significant abnormal findings except overweight and obesity should be discussed with the Sponsor.

Additional physical examination to assess subject's safety will be performed on study visit on Day 28.

#### 6.1.5. Vital Signs and Measurements

Subjects' vital signs will be measured at screening Day1 (performed 28 through 7 days prior to baseline) in order to ensure compliance with study inclusion criteria.

Vital signs measurements will include systolic and diastolic sitting position blood pressure, pulse rate, respiratory rate, and body oral temperature.

Additional vital signs measurements to assess subject's safety will be performed at baseline visit (Day 0) prior to drug injection,  $2h \pm 30$ min following drug injection, the following day (Day 1) after drug injection ( $24h \pm 2h$ ) and on study visits every 7 days thereafter, i.e., Day 7, Day 14 etc.

Additional pulse rate measurements to assess subject's safety will be performed at baseline visit (Day 0) prior to drug injection and 1h, 2h, 4h, 8h, 12h, 24h following injection in the opposite hand of blood sampling.

#### **6.1.6.** Anthropometric Measurements

Subjects' anthropometric measurements will be measured at screening Day 1 (performed 28 through 7 days prior to baseline) in order to ensure compliance with study inclusion and exclusion criteria. Anthropometric measurements will include height, weight, waist circumference and hip circumference. All anthropometric measurements will be measured in the morning following 10-12hr fast (overnight) and according to the Center for Disease Control (CDC) Anthropometry Procedures Manual of the National Health and Nutrition Examination Survey (NHANES) January 2007 edition (9).

Additional anthropometric measurements (apart from height) will be performed at Screening Day 2 before the MRI to ensure compliance with study inclusion and exclusion criteria, at -clinic admission visit (Day -1) and on study visit on Day 28. In subjects that are followed for over than 28 days, anthropometric measurements (apart from height) will be conducted on visit days attended at the study site every 28 days for a maximum period of additional 5 months. Additional weight measurements will be performed on weeks when weight is not measured at the site visits. In this case, weight will be measured by the subjects at their homes once a week in the morning following 8-12hr fast (overnight) and at bedtime. Subjects will be given a diary to record their weight.

### 6.1.6.1. Weight

Subjects' Weight will be measured in order ensure compliance with exclusion criteria and to calculate the BMI and ensure compliance with study inclusion criteria ( $27.5 < BMI \le 34.9$ ).

The subject will be instructed to stand completely still in the center of the scale platform with the feet close together hands at the sides and looking straight ahead. The weight measurement will be taken for the electronic readout and is recorded in kilograms to one digit after the decimal point.

## 6.1.6.2. Height

Subjects' Height will be measured in order to calculate the BMI and ensure compliance with study inclusion criteria  $(27.5 < BMI \le 34.9)$ .

The standing height or stature measurement is an assessment of maximal vertical size. This measure is for persons who are able to stand unassisted. Standing height is measured with a fixed stadiometer with a vertical backboard, a fixed floorboard, and movable headboard. Hair ornaments, jewelry, buns, braids and cornrows should be moved or removed from the top of the head in order to measure stature properly. The subject will be instructed to stand on the floorboard with the heels of both feet together, touching the base of the vertical board. The toes are pointed slightly outward at approximately a  $60^{\circ}$  angle. Body weight is evenly distributed with both feet flat on the floor. The technician will check the position of several points of body contact with the vertical board. The first contact point is the heels, followed by the buttocks, the scapula or shoulder blades, and finally the back of the head. Depending on the overall body conformation of the individual, all points may not touch. In such case, the trunk of the body should be positioned vertically above the waist with the arms and shoulders relaxed. The head should be aligned in the Frankfort horizontal plane. The head is in the Frankfort Plane when the horizontal line from the ear canal to the lower border orbit of the eye is parallel to the floor and perpendicular to the vertical backboard. Many people will assume this position naturally, but for some it may be necessary to make a minor adjustment. If required the technician may gently tilt the head up or down until proper alignment is achieved with the eyes looking straight ahead. Once correctly positioned the headboard is lowered. The subject is instructed to take a deep

breath and stand as tall as possible. A deep breath allows the spine to straighten yielding a more consistent and reproducible stature measurement. The headboard is positioned firmly on top of the head with sufficient pressure to compress the hair. The measurement will be read in centimeter and recorded in meters.

#### 6.1.6.3. **BMI**

Subjects' BMI will be calculated in order to ensure compliance with study inclusion criteria  $(27.5 < BMI \le 34.9)$  by the equation below:

BMI = weight (in kilograms)/ (height) (in meters)

BMI will be computed to one digit after the decimal point

### 6.1.6.4. Waist Circumference

Subjects' Waist Circumference will be measured in order calculate the WHR to ensure compliance with study inclusion criteria (WHR  $\geq$  0.9).

The subject will be instructed to gather his gown shirt above the waist, cross the arms, and place the hands on opposite shoulders. If necessary, lower the pants and underclothing to slightly below the waist. The technician will stand on the subject's right side and will palpate the hip area to locate the right ilium of the pelvis. With a cosmetic pencil, draw a horizontal line just above the uppermost lateral border of the right ilium. Cross this mark at the midaxillary line which extends from the armpit down the side of the torso. If it is difficult to find the iliac crest, such as on subjects with larger waists, then begin inferior to the midaxillary line (toward the subject front) and palpate the ilium upward to the midaxillary line until the uppermost part of the bone is found. Extend the measuring tape around the waist. Position the tape in a horizontal plane at the level of the measurement mark. Check that the tape sits parallel to the floor and lies snug but does not compress the skin. Always position the zero end of the tape below the section containing the measurement value. Take the measurement in centimeters to the nearest 0.1 cm at the end of the subject normal expiration (one digit after the decimal point).

#### 6.1.6.5. Hip Circumference

Subjects' Hip Circumference will be measured in order calculate the WHR to ensure compliance with study inclusion criteria (WHR  $\geq$  0.9).

The subject will be instructed to stand upright with feet together and weight evenly distributed. The buttocks or hip circumference is the only measure that is not taken directly on the skin. The assistant technician stands in front of the subject and gathers the fabric of the pants. The thumbs and index fingers hold the folded sides of the pants snugly. This minimizes the amount of material included in the measurement and helps to define the maximum protuberance of the buttocks when viewed in profile. The technician is positioned on the right side with eye level at

the hip region of the subject. The measuring tape is place around the hips and anchored at the maximum protuberance of the buttocks. The assistant then releases the folds of the pants and helps to adjust the tape so it is in a horizontal plane. The measuring tape is held snugly, but not pulled tight. The measure is recorded in centimeters to the nearest 0.1 cm (one digit after the decimal point).

### 6.1.6.6. Waist to Hip Ratio (WHR)

Waist to Hip Ratio (WHR) will be calculated in order to ensure compliance with study inclusion criteria (WHR  $\geq$  0.9) by the equation below:

WHR = Waist Circumference (in centimeters) / Hip circumference (in centimeters)

The WHR will be computed to two digits after the decimal point.

## 6.1.7. Serology Assays

Assays for Hepatitis C virus (HCV), Hepatitis B virus (HBV) and Human immunodeficiency virus (HIV) will be conducted at screening Day 1 (performed 28 through 7 days prior to baseline) in order to ensure compliance with study inclusion criteria.

### 6.1.8. Clinical Laboratory Tests

Clinical laboratory tests will be conducted at screening Day 1 (performed 28 through 7 days prior to baseline) in order to ensure compliance with study inclusion and exclusion criteria. Additional studies will be conducted on different study visits according to schedule as written below. Clinical laboratory tests performed on Clinic Admission visit are performed in order to establish a baseline except from the following tests that are performed to confirm eligibility: urine drug screen and clinical significant results that the PI feels will risk the subject.

The maximum total blood volume will be 30 -100 mL per visit. Every out-of-range value will be assessed by a physician and deemed as either clinically significant (CS) or clinically not significant (CNS). Values that represent a change from baseline in subject's medical status according to the laboratory normal ranges will be adequately documented as an adverse event (AE) as described in Section 9.

### 6.1.8.1. Hematology

Hematology tests will be conducted at screening Day 1 (performed 28 through 7 days prior to baseline) in order to ensure compliance with study inclusion criteria. Additional Hematology testing will be conducted to assess subject's safety on -clinic admission visit (Day -1), at  $24hr \pm 2h$  following injection and on study visit Day -1, 1, 3, 7, 14 and 28.

Hematology tests will include Complete blood count (CBC) (including White blood cells [WBC] differential values) and coagulation tests: White blood cells (WBC), Red blood cells (RBC),

Hemoglobin, Hematocrit, Mean corpuscular volume (MCV), Mean corpuscular hemoglobin (MCH), Mean corpuscular hemoglobin concentration (MCHC), Red cell distribution width (RDW), Platelets, Mean platelet volume (MPV), Fibrinogen, D-dimer, International normalized ratio (INR), Partial thromboplastin time (PTT) and Prothrombin time (PT).

#### 6.1.8.2. Serum Chemistry Analysis

Testing of blood chemistry values will be conducted at screening Day 1 (performed 28 through 7 days prior to baseline) in order to ensure compliance with study inclusion criteria. At screening Day 1, subjects should be notified to come fasting (10-12 hours of fast) for fasting glucose, blood test.

Additional fasting glucose, insulin, leptin, lipid profile blood tests will be conducted at clinic admission visit (Day -1) and on study visit Day 28 and every 28 days during follow-up period.

Additional Serum Chemistry testing will be conducted at clinic admission visit (Day -1) to establish baseline values,  $24hr \pm 2hr$  following injection and on study visit Day -1, 1, 3, 7, 14 and 28.

Serum chemistry will include: Sodium, Calcium, Potassium, Phosphorus, Glucose, Liver enzymes (Aspartate aminotransferase [AST], Alanine aminotransferase [ALT], Lactate dehydrogenase [LDH], Creatine-kinase MM [CK-MM], Gamma-glutamyltransferase [GTTP], Alkaline phosphatase [ALP]), Bilirubin, Creatinine, Urea/Blood urea nitrogen [BUN], Total protein, Albumin, Amylase, Creatine phosphokinase [CPK]

Lipid profile will include: (Triglycerides [TG], High-density lipoprotein [HDL], Low-density lipoprotein [LDL], Total-cholesterol [TC] and Free-fatty-acids [FFA]).

In case of CK-MM >x5 ULN, subjects will undergo clinical assessment for symptoms and alternative causes, and renal function will be assessed (including urinalysis).

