#### Results:

This was a dose escalation exploratory clinical trial of RZL-012, a first-in-class, new chemical entity.

RZL-012 was generally found to be safe in all cohorts. There were no clinically significant changes in vital signs, ECG and almost all blood laboratory tests. Most AEs associated with RZL-012 injection occurred confined to the injection site and were transient. Biopsy from the injected site revealed no damage to the skin 56 days following RZL-012 injection. The only significant local AE was an abscess in one subject in the lower abdomen on the injected side, but at a considerable distance from the site of injection.

In another patient, a severe elevation of ALT blood levels and a moderate elevation of AST blood levels were seen 14 days following injection. This elevation was transient (resolved within 14 days). In light of the pre-clinical findings (increased AST blood levels in female rats sacrificed on Day 2 following RZL-012 injection) and in light of the findings in this clinical trial, Raziel therefore plans to monitor closely (on 24hr, Day 3, Day 7, Day 14, Day 21, Day 28 and will follow further if necessary) liver functions in the next clinical trial. There were no other systemic clinically significant AEs.

The exploration of thermogenesis induction by RZL-012 in humans was successful. A raise in temperature at the injection site was mostly evident in cohort 3 (the highest dose) at Day 14 or Day 21 following injection in RZL-012 treated subjects only. This change in temperature was captured and recorded by the infra-red camera.

Although not statistical significant, a drop in the change from baseline in Subcutaneous Fat Mass (SFM) ratio (treated/control) over time by MRI in RZL-012 treated subject of cohort 3 was evident in 5 of 6 treated subjects. The drop in subcutaneous fat associated with a drop in weight (more than 1 kg) and BMI when compared to baseline and is evident in 4 of 6 RZL-012 treated subjects of cohort 3 on Day 28 and/or Day 56, while controls gained weight and increased BMI.

Biopsy did not yield enough tissue (because punch biopsy did not penetrate deep enough to reach the remodeled tissue), and therefore, it was not possible to demonstrate that thermogenesis is due to adipose tissue remodeling by.

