**Table 2: Subject Information and Timeframes** 

Information	Timeframe	Follow-up Timeframe
Informed Consent Form	Signed prior to any study dedicated procedure	
Medical History and Concomitant Medications	At screening visit and at clinic admission visit (Day -1)	
Physical examination	At screening Day1 visit and at Day 28	
Vital Signs	At screening Day 1 visit and at Days 0 (pre and following injection), 1, 7, 14, 21, 28	
Pulse rate	At Day 0 (pre and following injection) and at day 1	
ECG	At screening Day 1 visit, at Day 0 (following injection) and at Days 1, 14, 28	
Anthropometric Measurements: weight, height (screening only), BMI, waist circumference, hip circumference	At screening Day 1 visit, screening Day 2, clinic admission visit (Day-1) and at Day 28	Every 28 days. On Days 56, 84, 112, 140, 168
Weight – measured at home by the subjects at morning (8-12h fast) and at bedtime	At Days 7, 14 and 21	Every week when not visiting the site
Draize Score at the Injected Site	At screening Day 1 and at Days 0 (pre- and following injection), 1, 7, 14, 21, 28	Every 28 days.
Serology assays (HBV, HCV and HIV)	At screening day1 visit	
Urine drug screen	At screening Day 1 visit and at clinic admission visit (Day -1)	
Serum chemistry	At screening Day 1, at clinic admission visit (Day -1) and at Day 1, 3, 7, 14 and 28	
Hematology	At screening Day 1, at clinic admission visit (Day -1) and at Day 1, 3, 7, 14 and 28	
Fasting Glucose	At screening Day 1	
Fasting Glucose, Insulin, Leptin, Lipid Profile and FFA	At clinic admission visit (Day -1) and at Day 28	Every 28 days. On Days 56, 84, 112, 140, 168
Urinalysis	At screening Day 1 visit and at Days 14, 28	

Information	Timeframe	Follow-up Timeframe
Cytokines and inflammatory markers— in subjects from the 2 nd , 3 rd and 4 th cohorts	At clinic admission visit (Day -1) visit and at Days 7, 14, 21 and 28	
Histamine	At clinic admission visit (Day -1), and at Day 1, 3 and 14	
Pharmacokinetics in subjects from all cohorts	At Day 0-1	
Photography of the Injected Sites	At screening Day 1 visit and at Days 1, 7, 14, 21, 28	Every 28 days. On Days 56, 84, 112, 140, 168
Thermal Imaging	At screening Day 1 visit,at clinic admission visit (Day - 1)and at Days 1, 7, 14, 21, 28	On Day 56

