Infra-Red thermal imaging of the injected site -for 3 rd and 4 th cohort or in cohort 2 if 2 subjects experience intolerable side effects will in cohort 3) k											Every 28 days
Serum Chemistry, Hematology c	X		X		X	X	X	X		X	
Histamine levels d			X		X	X		X			
Urinalysis	X							X		X	
Pharmacokinetics f				Pre e X post e	X						
Draize score at the injected site g	X			Pre e X post e	X		X	X	X	X	Every 28 days
Vital signs h	X			Pre e X post e	X		X	X	X	X	
Injection of RZL-012				X							
ECG i	X			X post e	X			X		X	
Pulse rate j				Pre e X post e	X						
Adverse event assessment					X→						Every 28 days

Study Procedure	Screening Day 1	Screening Day 2	Clinic Admission	Baseline (Treatment)	Visit Schedule (Days 1 to 28)						Follow-up Schedule for the highest dose cohorts  (Days 29 - 168)
Study Day a	Day a -(- 28) through Day (-7)	Day a -(-14) through Day (-2)	Day (-1)	Day a 0	Day 1	Day 3	Day 7	Day 14	Day 21	Day 28	Day 56, 84, 112, 140, 168
Adverse event assessment by phone for cohorts 1 and 2											On Day 84 and 112
Subjects diary recording weight							X	X	X		On weeks when not visiting the site
Biopsy – In subject of cohort 3 (or in cohort 2 if 2 subjects experience intolerable side effects in cohort 3) k,1											On Day 56

- a. Study day is based on Day 0 defined as the day of RZL-012 injection.
- b. Inflammatory markers and cytokines from the 2nd, 3rd and 4th cohorts (on 6 RZL-012 treated and 2 placebo treated subjects in each cohort): **CRP**, Adiponectin, CD-163, Interleukin [IL]-1β, IL-4, IL-6, IL-10, IL12p70, IL-13, IL-23, Tumor necrosis factor [TNF] α and TGFβ1.
- c. CBC, coagulation, serum chemistry analysis, renal and liver function, urinalysis, CPK, amylase measurement: before injection, 14d and 28d following injection
- d. Histamine blood level measurement: clinical admission, following drug injection (24h ± 2h), 3d and 14d following injection
- e. Pre/post refers to before/after injection respectively
- f. Pharmacokinetics at the given time points: 0, 30, 60 min, 2h, 3h, 4h, 6h, 8h, 12h, 16h, 24h, 30h in subjects from all cohorts. Pharmacokinetics will not be conducted in the fourth cohort as the injected dose is divided in 2 clusters 2 weeks apart.

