Study Procedure	Screening Day 1	Screeni ng Day 2	Clinic Admissi on	Baseline (Treatme nt)	Visit Schedule (Days 1 to 28)			(8)	Follow- up Schedu le for the highest dose cohorts  1 (Days 29 - 168)		
Study Day a	Day a -(- 28) throug h Day (-7)	Day a -(- 14) through Day (-2)	Day (-1)	Day a 0	Da y 1	Da y 3	Da y 7	Day 14	Da y 21	Da y 28	Day 56, 84, 112, 140, 168
Draize score at the injected site g	X			Pre e X post e	X		X	X	X	X	Every 28 days
Vital signs h	X			Pre e X post e	X		X	X	X	X	
Injection of RZL-012				X							
ECG i	X			X post e	X			X		X	
Pulse rate j				Pre e X post e	X						
Adverse event assessment					X				→		Every 28 days
Adverse event assessment by phone for cohorts 1 and 2											On Day 84 and 112

Study Procedure	Screening Day 1	Screeni ng Day 2	Clinic Admissi on	Baseline (Treatme nt)	Visit Schedule (Days 1 to 28)			28)	Follow- up Schedu le for the highest dose cohorts (Days 29 - 168)		
Study Day a	Day a -(- 28) throug h Day (-7)	Day a -(- 14) through Day (-2)	Day (-1)	Day a 0	Da y 1	Da y 3	Da y 7	Day 14	Da y 21	Da y 28	Day 56, 84, 112, 140, 168
Subjects diary recording weight							X	X	X		On weeks when not visiting the site
Biopsy – In subject of cohort 3 (or in cohort 2 if 2 subjects experience intolerable side effects in cohort 3) k,l											On Day 56

[figure not shown]
- a. Study day is based on Day 0 defined as the day of RZL-012 injection.
- b. Inflammatory markers and cytokines from the 2nd, 3rd and 4th cohorts (on 6 RZL-012 treated and 2 placebo treated subjects in each cohort): CRP, Adiponectin, CD-163, Interleukin [IL]-1β, IL-4, IL-6, IL-10, IL12p70, IL-13, IL-23, Tumor necrosis factor [TNF] α and TGFβ1.
- CBC, coagulation, serum chemistry analysis, renal and liver function, urinalysis, CPK, amylase measurement: before injection, 14d and 28d following injection
- d. Histamine blood level measurement: clinical admission, following drug injection (24h ± 2h), 3d and 14d following injection
- e. Pre/post refers to before/after injection respectively

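### The Day 21 liver-function check announced in Protocol section 1.2.4 is missing from the operative schedule, so the planned interval after Day 14 is 14 days instead of 7

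*Protocol*

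**What the plan says.** Protocol section 1.2.4 (Clinical Studies, Results) reports a severe ALT and moderate AST elevation in one phase 0 subject, seen 14 days after injection. On duration it says: "This elevation was transient (resolved within 14 days". On other findings of this kind it says: "There were no other systemic clinically significant AEs". Citing this case and an AST increase in female rats on Day 2, it states that the sponsor "plans to monitor closely (on 24hr, Day 3, Day 7, Day 14, Day 21, Day 28 and will follow further if necessary) liver functions". The commitment concerns the study to follow phase 0, which in context is this one.

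ALT and AST are measured only as part of serum chemistry. The places that schedule that panel are:

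- Protocol 6.1.8.2: at 24 hours "following injection and on study visit Day -1, 1, 3, 7, 14 and 28".
- Protocol Table 2: "At screening Day 1, at clinic admission visit (Day -1) and at Day 1, 3, 7, 14 and 28", with no entry in the follow-up column.
- Protocol Appendix I, row "Serum Chemistry, Hematology": marked at Days 1, 3, 7, 14 and 28, with Day 21 empty and nothing after Day 28.
- SAP 5.4.4, same row: the same marks.

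Footnote c to that row gives a shorter list. The Protocol has "CPK, amylase measurement: before injection, 14d and 28d following injection" and the SAP has "amylase measurement: before injection, 14d and 28d following injection", although the row also marks Days 1, 3 and 7.

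**The concern.** A monitoring commitment made in response to a specific safety signal has not reached the schedule. Section 1.2.4 names Day 21 as a fixed time point and lists further follow-up, if needed, separately. A site working from Table 2 or Appendix I will not draw the sample as a planned assessment.

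The liver-enzyme rise was the one systemic clinically significant event reported in phase 0, and every dose here exceeds the phase 0 maximum. Two things are at stake:

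- planned detection of a rise that begins after a normal Day 14 panel and is gone by Day 28;
- a planned intermediate value for a rise already present at Day 14. The liver table in section 3.3.2 has a duration element (Grade 4 is more than 10 times the upper limit of normal persisting past 10 days), and liver events of Grade 3 or more count as intolerable.

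**Working it through.** The plan gives no figure of its own to reproduce. The check compares two sets of days and subtracts.

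**Panels**
- Section 1.2.4, post-dose to Day 28: {1, 3, 7, 14, 21, 28} = 6.
- Section 6.1.8.2, Table 2, Appendix I and SAP 5.4.4, post-dose to Day 28: {1, 3, 7, 14, 28} = 5.
- Difference: {21}.

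**Intervals** (visits to Day 28 have a ±1 day window, Protocol 6.2.5)

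| Interval | Nominal | Shortest | Longest |
|---|---|---|---|
| Day 14 to 28 (as scheduled) | 28 − 14 = 14 | 27 − 15 = 12 | 29 − 13 = 16 |
| Day 14 to 21 (with Day 21) | 21 − 14 = 7 | 20 − 15 = 5 | 22 − 13 = 9 |
| Day 21 to 28 (with Day 21) | 28 − 21 = 7 | 27 − 22 = 5 | 29 − 20 = 9 |

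A rise starting just after the Day 14 sample can therefore last almost 14 days and meet no planned sample, against almost 7 with Day 21 added. This needs no assumption about when rises begin. How often it would happen cannot be computed, because the documents give no distribution of onset or duration.

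**Persistence.** Take a value above a threshold at Day 14 and below it at Days 7 and 28, on nominal days, with one continuous episode. Onset lies between Days 7 and 14 and resolution between Days 14 and 28, so duration lies between 0 and 28 − 7 = 21 days. With a Day 21 value:
- below the threshold at Day 21: between 0 and 21 − 7 = 14 days;
- above it at Day 21: between 21 − 14 = 7 and 21 days.

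Day 21 narrows the range around the 10-day mark but does not settle it.

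**Dose.** The phase 0 maximum was 20 mg and doses here are 40 to 180 mg: 40/20 = 2 and 180/20 = 9 times.

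**Escalation review.** The DSMB reviews safety data to Day 14 of the last dosed subject, and the first three subjects in a cohort are dosed 7 days apart (Protocol 3.3.1). Even if no later subject were dosed after the third, at that review the second subject would be at Day 7 + 14 = 21 and the first at Day 14 + 14 = 28. If 7-day spacing also held for the couple and the triplet (an assumption), dosing would fall on study days 0, 7, 14, 21 and 28, with review on day 28 + 14 = 42. The couple would then be at Day 42 − 21 = 21. Five of eight subjects would have reached Day 21, and for the couple it would be the newest liver value.

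**Where the documented signals fall.** The phase 0 rise was seen at Day 14 and the rat AST increase at Day 2. Section 7.2 describes the AST increase in animals as reversible by Day 14. All of these lie at or before Day 14, where the schedule samples Days 1, 3, 7 and 14.

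**The case against.** A reader might infer that a rise after Day 14 is not covered at all, or that a repeat of the phase 0 event would be missed. The documents support neither.

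- Section 6.2.7 allows unscheduled visits at the investigator's discretion, with any procedure judged necessary. Redoing unusual results is a separate ground, so no abnormal result is required first. An investigator aware of the ALT/AST elevation listed in section 7.2 could order the tests at Day 21. The accurate description is that Day 21 is not guaranteed.
- A rise like that in phase 0 would be seen at Day 14. Section 6.1.8 then requires physician review of every out-of-range value, section 6.2.6 allows laboratory tests for unresolved events at termination, and section 9.5.1 has drug reactions above Grade 1 followed until they resolve, for up to 6 months.
- No documented signal falls in the gap. The only documented duration is a bound of 14 days, and a rise starting after Day 14 and lasting that long would still be present at Day 28.
- No stopping or escalation rule depends on a Day 21 value.
- Section 1.2.4 is background text, while the operative sections agree with one another. The documents do not show which side is the error. The Protocol supplied is numbered 001.2, whereas SAP 5.1.1 rests on V1.4. The SAP schedule still omits Day 21, but whether the sentence survived in V1.4 cannot be seen.

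These points stand, and they limit the consequence. They do not remove the mismatch. Discretionary testing is not the fixed time point that the sponsor named. Section 6.1.8.2 sets an explicit follow-up for CK-MM above 5 times the upper limit of normal but none for ALT or AST, and section 9.5.1 gives no retest interval. The 14-day figure is an upper bound, so shorter rises remain possible.

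**Conclusion.** The mismatch is certain: 5 planned post-dose panels against the 6 announced, and a 14-day interval (12 to 16 with windows) after Day 14, against 7 (5 to 9). The clinical consequence is narrow and hypothetical. It is confined to a rise that starts after Day 14 and clears before Day 28, and to the missing planned mid-course value for a rise already present at Day 14. No late rise has been reported, and no frequency of missed events should be attached to the gap.

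This rests on reading the next clinical trial in section 1.2.4 as this study, and on the Protocol version supplied. The Grade 3 cell of the liver table cannot be read in the available text, so nothing is drawn from it. Footnote c is a clerical matter, because its row, section 6.1.8.2 and Table 2 agree.

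Severity: minor to should-fix, as a cheap improvement.

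**What to change.** Add serum chemistry, at least ALT and AST, to the Day 21 visit in Protocol 6.1.8.2, Table 2 and Appendix I, and in SAP 5.4.4. Bring footnote c in both documents into line with its row. If Day 21 was dropped on purpose, correct section 1.2.4 and give the reason. That would remove the contradiction but not shorten the interval.

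The cost is a schedule amendment and one extra tube per subject: 4 cohorts × 8 = 32 at the planned sample size. The Day 21 visit already takes place in every cohort for thermal imaging (Protocol 6.1.12), and cohorts 2 to 4 already give blood then for cytokines (6.1.8.4). It is a new draw only for the 8 subjects of cohort 1.
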